5 SCHEDULE OF VISITS AND ASSESSMENTS

STUDY EVENTS FLOW CHART:

Study Procedure	Washout Cohort 2	Day 1 (Cohort 2)	Wk 4	Wk 12	Wk 18	Wk 24	Wk 30	Wk 36	Wk 44	Wk 52
Visit	Screening	Visit 7 (Week 12) of ARQ-151-201 Study (Cohort 1)	1	2	Phone Visit	3	Phone Visit	4	Phone Visit	5
Visit Window	-35 days		+/- 3 days	+/- 5 days	+/- 7 days	+/- 7 days	+/- 7 days	+/- 7 days	+/- 7 days	+/- 7 days
Informed consent	X ⁱ	X ⁱ								
Physical examination ^a		X ^h				X				X
I/E criteria	X	X								
Hematology, Serum Chemistries, and Urine Analysis	X	X ^h	X	X		X		X		X
12 lead ECG	X	X ^h				X				X
Vital signs, height, weight ^b		X ^h	X	X		X		X		X
IGA ^c , I-IGA, mPASI and BSA ^c	X	X ^h	X	X		X		X		X
C-SSRS, PHQ-8	X	X ^h	X	X		X		X		X
Urine pregnancy test ^d	X	X ^h	X	X		X		X		X
Local Tolerability Assessment ^e		X ^h	X	X		X		X		X
Dispense study medication kit ^f		X	X	X		X		X		
Dispense/review diary		X	X	X		X		X		X
Weigh study medication		X	X	X		X		X		X
Adverse event assessment ^g	X	X	X	X	X	X	X	X	X	X
Concomitant medications	X	X	X	X	X	X	X	X	X	X

^a Limited physical examination: skin, lungs, and heart only

^b Height will be collected at Day 1 only. Weight will be collected at all study visits. Subject to void prior to weight being taken. Remove any jackets, outerwear and shoes. Remove any objects of significant weight (i.e. cell phones, wallet, key chains). A 5% weight loss should be reported to the medical monitor.

^c IGA will be a 5-point scale ranging from clear (0) to severe (4). IGA should be completed prior to other physician assessments. Total BSA affected by psoriasis will be determined at each visit. A body diagram should be used to record areas of psoriasis involvement.

^d A urine pregnancy test will be administered to all females of child-bearing potential. A negative result is required for continued participation in the study, and results must be available prior to dispensing of study drug at each visit.

^e Local tolerability will be assessed by the clinic using the method of Berger and Bowman.

^f Kits will be dispensed based on %BSA affected. See IP Handling Manual for details.

- ^g Any emergent AEs will be followed in the clinic for up to one month at the Investigator's discretion until resolved or otherwise judged as clinically stable.
- ^h For Cohort 1, this data will be obtained from Week 12 of ARQ-151-201 Study and used as the Day 1 data for this long-term safety study (ARQ-151-202). If after ARQ-151-201 completion, subjects should complete the screening visit procedures. The Baseline values for Safety tabulations will be taken from the day that the subject received their first active study drug (across studies ARQ-151-201 and ARQ-151-202). Baseline values for efficacy will be those recorded on Day 1 of Study ARQ-151-201. For Cohort 2, Baseline evaluations will be obtained for all procedures and the Baseline/Screening version of the C-SSRS will be utilized at Screening. For Cohort 2, labs that are collected within 14 days of Baseline do not need to be repeated.
- ⁱ For Cohort 1, the consent will be signed after completion of Week 12 in ARQ-151-201. Cohort 2 will sign consent prior to any study-related procedures at the Screening Visit.

6 ABBREVIATIONS

Acronym	Full Name
AE	Adverse Event
AMP	Adenosine Monophosphate
AUC	Area Under the Curve
BSA	Body Surface Area
C _{max}	Maximum Concentration
COPD	Chronic Obstructive Pulmonary Disease
CRF	Case Report Form
C-SSRS	Columbia-Suicide Severity Rating Scale
CTCAE	Common Terminology Criteria for Adverse Events
DNA	Deoxyribonucleic Acid
ERB	Ethics Review Board
FDA	U.S. Food and Drug Administration
FOCBP	Female of Child Bearing Potential
GCP	Good Clinical Practices
HC	Health Canada
HCA	Alpha-Hydroxycinnamaldehyde
HPRT	Hypoxanthine-guanine Phosphoribosyl Transferase
IB	Investigational Brochure
IC ₅₀	Half Maximal Inhibitory Concentration
ICF	Informed Consent Form
ICH	International Conference on Harmonisation
IGA	Investigator Global Assessment
IND	Investigational New Drug
IRB	Institutional Review Board
LED	Light Emitting Device
IWRS	Interactive Web Response System
µg	Microgram
MedDRA	Medical Dictionary for Regulatory Activities
mITT	Modified Intent to Treat
mL	Milliliter
MMRM	Mixed effect Model Repeat Measurement
mPASI	Modified Psoriasis Area and Severity Index

Acronym	Full Name
MTD	Maximum Tolerated Dose
NCI	National Cancer Institute
NIH	National Institutes of Health
NOAEL	No Observed Adverse Effect Level
ng	Nanogram
NRS	Numerical Rating Score
PASI	Psoriasis Area and Severity Index
PDE-4	Phosphodiesterase 4
PHQ-8	Patient Health Questionnaire depression scale
PI	Principal Investigator
PK	Pharmacokinetics
PP	Per Protocol
PSD	Psoriasis Symptoms Diary
QD	Once Daily ("quaque die")
SAE	Serious Adverse Event
TEAE	Treatment Emergent Adverse Event
Th1	Type 1 T Helper Cell
Th17	Type 17 T Helper Cell
T _{max}	Time to reach maximum concentration
V79	Chinese hamster cell line

7 BACKGROUND AND RATIONALE

7.1 Introduction

Roflumilast is a phosphodiesterase 4 (PDE-4) inhibitor approved globally to reduce the risk of exacerbations in patients with severe chronic obstructive pulmonary disease (COPD) associated with chronic bronchitis. Roflumilast and its active metabolite, roflumilast N-oxide, are high affinity selective inhibitors of PDE-4 (a major cyclic-3',5'-adenosine monophosphate (cyclic AMP)-metabolizing enzyme), whose activity leads to accumulation of intracellular cyclic AMP. There are four different subtypes of PDE-4: PDE-4a, PDE-4b, PDE-4c, and PDE-4d, each with several isoforms (splicing variants). IC₅₀ values of both roflumilast and roflumilast N-oxide for the different PDE-4 isoforms and subtypes are mostly sub-nanomolar and single digit nanomolar ([Hatzelmann 2010](#)). The PDE-4 family of enzymes are the most prevalent phosphodiesterases in immune cells and inhibition of PDE-4 subtypes has been associated with anti-inflammatory effects in many biological systems.

Psoriasis is a chronic inflammatory skin disease characterized by raised, well-demarcated, erythematous oval plaques with adherent silvery scales. Numerous past reports have suggested a deficiency of cyclic AMP-dependent protein kinases in human psoriatic skin ([Brion 1986](#)). More recently, various cytokines produced by Th1 and Th17 cells have been shown to play a crucial role in the pathogenesis of psoriasis. It has been postulated that the anti-inflammatory effects of PDE-4 inhibitors may provide a beneficial therapeutic intervention in the treatment of chronic plaque psoriasis and recently Otezla[®] (apremilast), a PDE-4 inhibitor, has been approved for the oral treatment of chronic plaque psoriasis.

The past 15 years have witnessed a transformation in the systemic treatment of moderate to severe psoriasis with the advent of biological therapies. However, for patients with milder forms of disease, best treated with topical options, the therapeutic landscape really has not changed in several decades. Topical steroids come in all shapes and forms, but the lower potency steroids are not effective and the higher potency steroids are beset with issues of local skin atrophy and the potential for hypothalamic-pituitary axis suppression when applied over larger body surface areas and for prolonged periods of time. Vitamin D has been the other staple of topical psoriasis treatment but it is irritating, not suitable for use on the face or intertriginous areas, and its efficacy is rather modest. Hence, there is substantial medical need for additional topical approaches in the treatment of psoriasis. The study sponsor is developing a topical formulation of roflumilast for the treatment of chronic plaque psoriasis. Our Phase 2a results suggest that ARQ-151 may be a highly efficacious and well-tolerated topical treatment for psoriasis.

7.2 Preclinical Studies

Roflumilast was initially developed as a 500 µg tablet for oral therapy in patients with COPD, and as such has been thoroughly evaluated in nonclinical studies. The safety profile is well-established and the results of those studies are relevant to the dermal roflumilast (ARQ-151 cream) development program. Oral roflumilast (500 µg tablet) was approved by Health Canada as DAXAS[®] in December 2010 and by the US FDA as DALIRESP[®] in February 2011 for the treatment of COPD. The study sponsor is conducting nonclinical studies in which roflumilast is applied dermally to supplement the information available through the registration and labeling of

oral roflumilast and specifically to support dermal clinical trials. Summaries of these new data from dermal studies and existing data from the prior oral/systemic studies follow. In addition, since roflumilast N-oxide is a major active metabolite, some studies were conducted on the metabolite.

The dermal nonclinical program for ARQ-151 cream followed current International Conference on Harmonisation (ICH) guidelines. [REDACTED]

7.2.1 Repeat-Dose Toxicity

[REDACTED]

[REDACTED]

[REDACTED]

7.2.2 Oral (Systemic) Studies of Roflumilast and N-Oxide Metabolite

[REDACTED]

7.2.3 Reproductive Toxicity

[REDACTED]

[REDACTED]

7.2.4 Genotoxicity

[REDACTED]

[figure not shown]
7.2.5 Carcinogenicity

[REDACTED]

7.2.6 Special Toxicity: Local Tolerance of Topical Formulation

7.2.7 Conclusions on Toxicity Findings

[REDACTED]

[REDACTED]

[REDACTED]

7.3 Clinical Studies

7.3.1 Topical Roflumilast Cream

This will be the third study of topical ARQ-151 cream in the human population.

7.3.2 Phase 1/2a Study of Topical ARQ-151 Cream

[REDACTED]

[REDACTED]

[REDACTED]

[REDACTED]

[REDACTED]

[REDACTED]

Efficacy and safety results of ARQ-151-101 are as follows:

- [REDACTED]

- [REDACTED]
- [REDACTED]
- [REDACTED]

[figure not shown]
7.3.3 Phase 2b Study of Topical ARQ-151 Cream

7.3.4 Oral Roflumilast Tablet

[figure not shown]
Oral roflumilast ([DALIRESP®](#), [DAXAS®](#), a 500 µg tablet) has been approved globally for the treatment of COPD and has been evaluated in nine Phase III/IV randomized double-blind clinical trials ([Wedzicha 2016](#)). Overall, the safety of oral roflumilast has been well established in its targeted population of mostly middle- and upper-aged individuals who currently smoke cigarettes or have smoked them extensively in the past. Adverse events (AEs) reported with roflumilast tablets have been consistent with those expected for oral PDE-4 inhibitors. In a pooled analysis of safety data from 6-month and 1-year clinical trials (N=8630), the most common AEs were diarrhea, weight loss and nausea. Other AEs reported more frequently with roflumilast treatment than with placebo were back pain, influenza, insomnia and decreased appetite ([Michalski 2012](#), [Wedzicha 2016](#)).

In addition to the self-reported cases of weight loss in the 6-month and 1-year oral trials, clinically significant weight loss was also reported in two prospective studies that evaluated weight ([Michalski 2012](#)).

Psychiatric-related AEs were also greater in patients treated with roflumilast tablets (5.9%) compared to those treated with placebo (3.3%). The most common psychiatric-related AEs were insomnia, depression and anxiety. A small number of cases of completed suicide and suicide ideation have been reported in patients taking oral roflumilast in clinical trials and also during post-marketing experience ([Michalski 2012](#)).

7.4 Rationale for Development

7.4.1 Dose Selection

[REDACTED]

[REDACTED]

[REDACTED]

7.4.2 Risks and/or Benefits to Subjects

[REDACTED]

[REDACTED]

[REDACTED]

8 STUDY OBJECTIVE AND ENDPOINTS

8.1 Study Objective

The objective of this study is to assess long-term safety in a multicenter, open-label, 52-week study in subjects treated with ARQ-151 cream 0.3% after completing a 12-week Phase 2b study (ARQ-151-201) Cohort 1 and non ARQ-151-201 subjects (Cohort 2).

8.2 Study Endpoints

8.2.1 Primary Endpoint

The primary endpoint will be analysis of safety monitored through application site assessments in the clinic using the method of Berger and Bowman, clinical laboratory testing, 12-lead ECGs, PHQ-8, C-SSRS and adverse events. Two primary endpoint analyses are planned:

- Occurrence of Treatment Emergent Adverse Events
- Occurrence of Serious Adverse Events

8.2.2 Secondary Endpoints

The secondary endpoints are related to efficacy and will include:

- Proportion (%) of subjects achieving an Investigator Global Assessment (IGA) of clear or almost clear, as observed at Week 12 and subsequent scheduled visits.
- In subjects who achieve 'clear' scores for IGA, I-IGA (if applicable **and** mPASI (Modified Psoriasis Area Severity Index) and stop treatment to all lesions, time to re-starting study drug (duration of response).
- Proportion (%) of applicable subjects with intertriginous area involvement, 'I-IGA' score of 'clear' or 'almost clear' at week 12 and subsequent visits
- Proportion (%) of subjects achieving a 75% reduction from Baseline of Modified Psoriasis Area Severity Index-75 (mPASI-75) at weeks 12, 24, 36 and 52 as compared to Baseline.

9 INVESTIGATIONAL PLAN

9.1 Overall Study Design and Plan

This is an open-label, long-term safety study of ARQ-151 cream 0.3% in subjects with chronic plaque psoriasis involving between 0 and 25% BSA. Eligible subjects will enroll into the long-term safety study on the same day as the Week 12 visit for the previous study (ARQ-151-201) for Cohort 1 and on Day 1 for non ARQ-151-201 subjects in Cohort 2. Study medication will be applied by the subjects topically QD for 52 weeks at home.

A total of up to approximately 300 subjects (Cohort 1) and up to approximately 100 non ARQ-151-201 subjects (Cohort 2) will be enrolled at approximately 30 study sites in the United States and Canada. Subjects will be adult (≥ 18 y/o) males or females with chronic plaque psoriasis. Periodic clinic visits will include assessments for clinical safety, application site reactions evaluated in the clinic using the method of Berger and Bowman, disease improvement or progression, and IGA.

9.2 Subject Participation

Subject participation involves a minimum of five clinic visits at Week 4, Week 12, Week 24, Week 36 and Week 52 of treatment. There will be three phone visits conducted at Weeks 18, 30 and 44. The Day 1 visit of this study will be Week 12 of the ARQ-151-201 study (Cohort 1) and Day 1 for Cohort 2. The Baseline values for Safety tabulations will be taken from the day that the subject received their first active study drug. Baseline values for efficacy will be those recorded on Day 1 of Study ARQ-151-201. The anticipated maximum duration of subject participation is about 52 weeks. Subjects in the ARQ-151-201 study that choose to participate in the long-term extension study will transition directly into the ARQ-151-202 study at the Day 1 visit (Week 12 of Study ARQ-151-201).

9.3 Randomization

This is an open-label study and all subjects will be treated with ARQ-151 cream 0.3% QD to psoriatic plaques up to a maximum application area of 25% BSA.

9.4 Numbering of Subjects

All screened subjects enrolled will retain their unique five-digit subject ID number previously assigned during the ARQ-151-201 study (Cohort 1). For Cohort 2 subjects will be numbered with the 2 digit site number and a three digit subject number starting with 500.

The clinical site is responsible for maintaining a current log of subject ID number assignments and study drug kits assigned to that subject. The subject ID number is required to be entered on all clinical study documentation (e.g., case report forms, labeling of clinical materials and sample containers, investigational product accountability logs, etc.).

9.5 Blinding

This is an open-label study and no blinding is planned.

9.6 Selection of Patient Population

9.6.1 Inclusion Criteria

All Subjects

Subjects must fulfill all of the following inclusion criteria to be eligible for participation in the study:

1. Participants legally competent to sign and give informed consent
2. Males and females ages 18 years and older
3. Females of childbearing potential (FOCBP) must have a negative urine pregnancy test at all study visits. In addition, sexually active FOCBP must agree to use at least one form of highly effective contraception throughout the trial. Highly effective forms of contraception include: oral/implant/injectable/transdermal contraceptives, intrauterine device, and partner's vasectomy. If barrier methods are used (e.g., condom with spermicide, diaphragm with

spermicide), then 2 forms of conception are required. The use of abstinence as a contraceptive measure is acceptable as long as this is a consistent part of a lifestyle choice and a backup method has been identified if the subject becomes sexually active.

4. Post-menopausal women with spontaneous amenorrhea for at least 12 months or have undergone surgical sterilization (permanent sterilization methods include hysterectomy, bilateral oophorectomy, hysteroscopic sterilization, bilateral tubal ligation or bilateral salpingectomy).

Cohort 1 Only

5. Subjects with chronic plaque psoriasis who met eligibility criteria for ARQ-151-201, successfully completed ARQ-151-201 through Week 12, and enroll into this long-term safety study on the Week 12 visit of the previous study (ARQ-151-201).

Cohort 2 Only

6. Clinical diagnosis of psoriasis vulgaris of at least 6 months duration as determined by the Investigator.
7. Psoriasis vulgaris on the face, extremities, trunk, and/or intertriginous areas involving 2% to 25% of BSA (excluding the scalp, palms and soles).
8. An Investigator's Global Assessment of disease severity (IGA) of at least Mild ('2') at Day 1.

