Inclusion Criteria All Subjects	
 1. Participants legally competent to sign and give informed consent 2. Males and females ages 18 years and older 3. Females of childbearing potential (FOCBP) must have a negative urine pregnancy test at all study visits. In addition, sexually active FOCBP must agree to use at least one form of highly effective contraception throughout the trial. Highly effective forms of contraception include: oral/implant/injectable/transdermal contraceptives, intrauterine device, or partner's vasectomy. If barrier methods are used (e.g., condom with spermicide, diaphragm with spermicide), then 2 forms of conception are required. The use of abstinence as a contraceptive measure is acceptable as long as this is a consistent part of a lifestyle choice and a backup method has been identified if the subject becomes sexually active. 4. Post-menopausal women with spontaneous amenorrhea for at least 12 months or have undergone surgical sterilization (permanent sterilization methods include hysterectomy, bilateral oophorectomy, hysteroscopic sterilization, bilateral tubal ligation or bilateral salpingectomy).
Inclusion Criteria Cohort 1 Only	
 5. Subjects with chronic plaque psoriasis who met eligibility criteria for ARQ-151-201, successfully completed ARQ-151-201 through Week 12, and are able to enroll into this long-term safety study on the Week 12 visit of the previous study (ARQ-151-201).
Inclusion Criteria Cohort 2 Only	
 6. Clinical diagnosis of psoriasis vulgaris of at least 6 months duration as determined by the Investigator. 7. Psoriasis vulgaris on the face, extremities, trunk, and/or intertriginous areas involving 2% to 25% of BSA (excluding the scalp, palms and soles). 8. An Investigator's Global Assessment of disease severity (IGA) of at least Mild ('2') at Day 1.
Exclusion Criteria All Subjects	
 1. Subjects that use any Excluded Medications and Treatments (see Table 1). 2. Subjects currently taking lithium or antimalarial drugs. 3. Planned initiation or changes to concomitant medication that could,

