10 STUDY PROCEDURES

10.1 Safety Assessments

The Schedule of Visits and Assessments (see [Section 5](#)) summarizes the clinical procedures to be performed at each visit. Individual clinical procedures are described in detail below. Additional evaluations/testing may be deemed necessary by the PI and/or the Sponsor for reasons related to subject safety.

This study assesses the long-term safety of ARQ-151 cream 0.3%. Safety will be monitored through application site assessments in the clinic using the method of Berger and Bowman, physical examination, clinical laboratory testing, 12-lead ECGs, PHQ-8, C-SSRS and AEs as outlined in the Schedule of Visits and Assessments ([Section 5](#)). If deemed necessary, additional safety assessments will be performed at the discretion of the Investigator.

Screening Visit (Cohort 2)

Within 35 days prior to the first dosing, non ARQ-151-201 subjects will be provided details of study requirements and sign an informed consent. Each subject will undergo psoriatic plaque assessments, a physical examination, vital sign measurements (blood pressure, heart rate, and temperature), PHQ-8, C-SSRS, and laboratory tests: hematology, chemistry, urinalysis and a pregnancy test for female subjects of child bearing potential.

Screening should occur for Cohort 1 subjects if they have completed ARQ-151-201 previously.

All screened subjects will receive a screening number and be entered into the electronic subject tracking system.

Day 1 Visit

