11.1.1 Baseline Definition

Cohort 1 baseline value for each parameter will be defined as the last observation prior to first dose of ARQ-151 cream 0.3% or ARQ-151 cream 0.15%. For subjects receiving either active study drug in ARQ-151-201, the baseline values from ARQ-151-201 will be considered the baseline values for calculations in ARQ-151-202. For subjects receiving Vehicle in ARQ-151-201, baseline values will most commonly be from the Week 12/study exit visit of ARQ-151-201. If subjects choose to enroll in this study, study procedures will not be repeated; study sites will carry over the information from the ARQ-151-201 study (Week 12 visit) to the Day 1 visit for this study. Baseline values for IGA, however, will be taken from Day 1 of Study ARQ-151-201 for all subjects.

Cohort 2 baseline value for each parameter will be collected on Day 1.

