12.5 Protocol Amendments and Deviations

No change or amendment to this protocol may be made by the investigator or Sponsor after the protocol has been agreed to and signed by all parties unless such change(s) or amendment(s) has (have) been agreed upon by the investigator and Sponsor. Any change agreed upon will be recorded in writing, and the written amendment will be signed by the investigator and Sponsor. Institutional review board approval is required prior to the implementation of an amendment, unless overriding safety reasons warrant immediate action, in which case the IRB(s) will be promptly notified.

No deviation from the protocol will be made except to protect the life or physical well-being of a subject in an emergency. Except in such emergencies, prior approval of the Sponsor, and the IRB, is required before deviations from the planned protocol. All protocol deviations that occur during the study will be documented and reported to Sponsor and to the IRB(s), if applicable, according to regulations. Further details about the documentation, evaluation, and follow-up of protocol deviations are detailed in this study's clinical monitoring plan.

No waivers to inclusion/exclusion criteria will be granted; subjects need to meet all criteria, exactly as specified, to be enrolled. Additionally, prospective deviations from the protocol or investigational plan are not permitted except to protect the life or physical well-being of a subject in an emergency. Deviations that occur unintentionally or are the result of action by the subject must be documented and reported to the IRB(s), if applicable, according to regulations. Further details about the documentation, evaluation, and follow-up of protocol deviations are detailed in this study's clinical monitoring plan.

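### Cohort 1 must enrol at the ARQ-151-201 Week 12 visit, yet the protocol also provides for later entry, leaving late entrants ineligible as written and without a defined Day 1 record or look-back for most psoriasis treatments

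*Protocol*

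**What the plan says.** **Entry tied to Week 12.** Protocol Section 9.6.1, criterion 5 (Cohort 1 only), requires that subjects "enroll into this long-term safety study on the Week 12 visit of the previous study", ARQ-151-201. Section 9.1 has eligible subjects "enroll into the long-term safety study on the same day as the Week 12 visit for the previous study", and Section 9.2 describes a direct transition in which Week 12 of ARQ-151-201 is Day 1 of this study. The Synopsis is slightly looser, asking for subjects who "are able to enroll into this long-term safety study on the Week 12 visit of the previous study (ARQ-151-201"). Section 12.5 closes the door on exceptions: "No waivers to inclusion/exclusion criteria will be granted; subjects need to meet all criteria, exactly as specified, to be enrolled".

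**Later entry provided for.** Section 10.1, under the Screening Visit, says: "Screening should occur for Cohort 1 subjects if they have completed ARQ-151-201 previously". Footnote h to the flow chart in Section 5 says: "If after ARQ-151-201 completion, subjects should complete the screening visit procedures".

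**Day 1 data.** Section 11.1.1 says that "study procedures will not be repeated; study sites will carry over the information from the ARQ-151-201 study" Week 12 visit to Day 1 of this study. Footnote h and the Day 1 text of Section 10.1 likewise use Week 12 results as Cohort 1 Day 1 data.

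**Prior treatment.** Table 2, exclusion 19 in Section 9.6.2 and the washout sentence in Section 10.1 are all confined to Cohort 2.

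**Treatment-free days.** For rollover subjects who had active cream in ARQ-151-201, Section 11.3 counts from the last treatment that began in that study to the next treatment in this one.

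**The concern.** The two late-entry sentences make sense only for a Cohort 1 subject who was not enrolled at Week 12, and that is the subject criterion 5 shuts out. A site cannot obey both. The same enrolment would be a planned case under one section and an eligibility deviation under another.

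Three analysis questions follow for anyone who enters late. Which values are their Day 1 record? What prior-treatment rule covers the interval between studies? How is that interval treated when time to relapse is computed? The Cohort 1 rules assume an interval of zero, and no passage sets a maximum.

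**Working it through.** The protocol gives no figure on this point, so the check is a comparison of passages, applied to one hypothetical Cohort 1 subject who completed ARQ-151-201 and presents some time later.

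1. **Eligibility.** Under 9.6.1 (criterion 5), 9.1 and 9.2, enrolment must coincide with the Week 12 visit. This subject fails that, and 12.5 allows no waiver. Under 10.1 and footnote h, the same subject is to be screened. Both sets of passages are current text, so the contradiction stands.

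2. **Day 1 record.** Under 11.1.1 the Week 12 values are carried over and nothing is repeated; the sentence is not limited to same-day entrants. Under footnote h the screening procedures are done. The subject then has two sets of pre-dose values, and no passage names the one that fills Day 1.

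3. **Baseline by prior arm.**
   - *Prior active:* 11.1.1 takes baseline from ARQ-151-201, so the gap does not affect it.
   - *Prior vehicle:* 11.1.1 defines baseline as the latest observation before the first active dose. That selects a new screening value where one exists. The carry-over sentence selects Week 12. The two rules can return different values for the same parameter.
   - *Weight:* the flow chart does not mark weight at Screening, and the screening text in 10.1 lists only blood pressure, heart rate and temperature among vital signs, although 10.1.2 says weight is taken at all study visits. A new pre-dose weight is therefore not assured, and weight feeds the shift table for changes above 5% in 11.2.3.

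4. **Prior treatment.** Three restrictions still bind the late entrant: exclusion 2 (use of Table 1 treatments, with no look-back period), exclusion 10 (oral roflumilast within 4 weeks) and the note to Table 1 on stable inhaled corticosteroids. The periods in Table 2 do not, because all three references to them are limited to Cohort 2. For other psoriasis treatments used and stopped in the gap, no look-back is stated.

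5. **Treatment-free days, prior-active rollovers.** Let g be the days from the last ARQ-151-201 application to the late Day 1, and d the days from Day 1 to the first application in this study. Section 11.3 gives T = g + d.
   - Same-day entrant: g is about 0, so T = d.
   - Late entrant who starts on Day 1: d = 0, so T = g.
   - Any late entrant: T is at least g, because study cream is first dispensed at Day 1 and retreatment under this protocol cannot be recorded sooner.

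   The gap therefore enters the Kaplan-Meier analysis day for day as time without relapse. For prior-vehicle rollovers the count starts at the end of initial treatment in this study, so the gap does not enter.

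**The case against.** The best defence is that footnote h states a general rule and then an exception: Week 12 data serve as Day 1, but someone who enters after completing ARQ-151-201 is screened. Section 11.1.1 merely repeats the general rule. The Synopsis wording can also be read as requiring only the ability to enrol at Week 12. This softens the Day 1 conflict to a missing statement of which record governs. It does not rescue eligibility: 9.6.1 has no such latitude, 9.1 says the same day, and even the Synopsis names the Week 12 visit.

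Two stronger readings are tempting and should not be adopted.

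- A reader might infer that prior-vehicle late entrants necessarily have an out-of-date safety baseline. Section 11.1.1 does not say so. Its definition is the latest pre-dose observation, and it says only that Week 12 will usually supply it. What stands is that the definition and the carry-over sentence can disagree.
- A reader might infer that late entrants face no restriction on prior or concurrent psoriasis treatment. Exclusions 2 and 10 and the inhaled-steroid note say otherwise, and eligibility and concomitant medications are checked at Screening. What stands is the absence of a look-back for the remaining treatments.

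It is also fair to say that the consequences are limited. The primary endpoints are occurrences of TEAEs and SAEs rather than changes from Day 1 values. Footnote h and 10.1 fix the Cohort 1 efficacy baseline at Day 1 of ARQ-151-201. All safety analysis is descriptive. Nor can one conclude that adverse events in the gap go uncollected: this protocol collects from consent, but the follow-up rules of ARQ-151-201 are not at hand.

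On treatment-free days, Section 8.2.2 limits duration of response to subjects who cleared and stopped all treatment. Section 11.3 does not repeat that condition for rollovers. If it applies, fewer late entrants are affected, but T is still at least g for each of them.

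**Conclusion.** The point holds as an internal contradiction that should be corrected. Criterion 5 with the no-waiver rule cannot be reconciled with the late-entry sentences in 10.1 and footnote h. If late entry happens, the Day 1 record is undefined, the prior-vehicle baseline can be read two ways, no look-back is stated for most psoriasis treatments used in the gap, and treatment-free time can be lengthened by the gap in prior-active rollovers.

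No size can be attached. The protocol gives about 300 as the planned Cohort 1 enrolment but not how many would enter late, how long the gaps would be, or the split by prior arm. Any count of ineligible subjects or affected baselines would be conjecture. If nobody enters late, the harm is confined to confusing text. A statistical analysis plan could settle the Day 1 source and the gap, but it could not cure the eligibility conflict.

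**What to change.** Choose one of two routes by amendment.

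- **No late entry:** delete the late-entry sentences in 10.1 and footnote h.
- **Late entry allowed:** reword criterion 5, and align the Synopsis, 9.1 and 9.2, to admit it within a maximum gap set by the sponsor. Then:
  - state that the newest pre-dose assessments are the Day 1 values and the prior-vehicle safety baseline, limit the carry-over in 11.1.1 to same-day entrants, and make clear whether weight is among those assessments;
  - have the sponsor reconcile which prior-medication rule applies to these subjects, since 9.6.2, Table 1 and Table 2 now leave it open;
  - flag late entrants in the dataset;
  - say in 11.3 how the enrolment gap is handled for prior-active rollovers, for example by reporting treatment-free days with and without flagged subjects.

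The cost is amendment wording and one analysis flag. Footnote h already calls for the screening assessments; the possible addition is a pre-dose weight.
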